I will report (within 24 hours) any serious adverse event that occurs during the study in accordance with the procedures described in Section 9 of the protocol.

[figure not shown]
[figure not shown]
[figure not shown]
I will allow the Sponsor, Raziel Therapeutics Ltd. and its agents, as well as the United States (US) Food and Drug Administration (FDA) and other regulatory agencies, to inspect study facilities and pertinent records at reasonable times and in a reasonable manner, ensuring subject confidentiality. If I am notified that this study is to be inspected by a regulatory agency, I will notify the Sponsor as soon as possible thereafter (no later than one week).

[name]  10/22/2019
Investigator's name Investigator's Signature Date

[figure not shown]
PROTOCOL SYNOPSIS

Protocol Number	RZL-012-FD-P2aUS-001
Protocol Title	An open label, phase 2a clinical trial for the evaluation of safety and efficacy of RZL-012 for the treatment of women with lipedema involving substantial fat above the knee or women and men with nodular Dercum's disease.
Study Phase	Phase 2a
Study Drug	RZL-012
Study Objectives	
Primary objective: Evaluation of the overall safety of RZL-012 following injection into the subcutaneous fat in patients with lipedema.
 
Secondary objective: Evaluation of local fat reduction, its extent, duration and tissue associated changes, in response to RZL-012 treatment, utilizing minimal invasive means (ultrasound) following subcutaneous injection of RZL-012 into fatty tissue below the skin.

Sample Size	12 subjects
Study Design	
This is an open label, 2 cohort clinical trial in women with lipedema with substantial fat above the knee or women and men with nodular Dercum's disease. Each cohort will have 6 subjects who will receive RZL-012.
 
 • The 1st cohort will be comprised of subjects with Dercum's disease • The 2nd cohort will be comprised of subjects with lipedema with substantial fat above the knee. 
Within each cohort, dosing of the subjects will progress consecutively from one individual to the other with a minimum of 7-days between subjects to assess safety. This study design will allow the physicians to monitor safety for at least 7 days prior to dosing the next subject. Cohort 2 will be conducted in a dose escalation manner and the decision to proceed to the next dose level will be made after reviewing all safety data collected by Day 14 within 2 ± 1 d of the last dosed subject. The trial will proceed within a cohort provided that no more than one subject experiences intolerable side effects in a cohort, and based on the decision made by the Principal Investigator (PI) and the Medical Monitor.

Study Population	Post-menopausal women no more than 65 years old, with lipedema involving substantial fat above the knee or nodular Dercum's disease in such women and in men 20- 65 years with nodular Dercum's disease.

Main Inclusion Criteria	
Subjects must meet all the following to be eligible for study participation:
 
1. Post-menopausal (at least 2 years) women no more than 65 years old, with lipedema involving substantial fat above the knee or nodular Dercum's disease in such women and in men 20 - 65 years with nodular Dercum's disease.2. For Dercum's disease subjects – at least 2 nodules to be injected of at least 2cm diameter, each, as determined by ultrasound3. For lipedema subjects - Significant subcutaneous fat above the knee as determined by circumference of 50cm4. Generally considered healthy according to medical history, physical examination, electrocardiogram (ECG) and laboratory evaluation with a special emphasis on metabolic parameters (fasting glucose concentration < 200 mg/dL, normal blood pressure).5. Subjects must be able to adhere to the visit schedule and protocol requirements and be available to complete the study.6. Subjects must sign an informed consent indicating that they are aware of the investigational nature of the study.
Main Exclusion Criteria	
Subjects meeting any of the following criteria will be excluded:
 
1. Unable to tolerate subcutaneous injection.2. Subjects with uncontrolled cardiac, hepatic, renal or neurologic/psychiatric disorders, that in the opinion of the investigator put the subject at significant risk, are not eligible.3. Positive blood screen for Hepatitis B surface antigen (HbSAg), Hepatitis C virus (HCV), or Human immunodeficiency virus (HIV), or positive urine screen for alcohol or drugs of abuse (unless prescribed by a physician).4. Subjects with a clinical history of primary or secondary immunodeficiency, autoimmune disease or subjects taking immunosuppressive drugs such as corticosteroids are ineligible.5. As a result of medical review, physical examination, the PI (or medically qualified nominee) considers the subject unfit for the study.6. Known sensitivity to components of the injection formulation.7. Prior wound, tattoo or infection in the treated area.8. Prior invasive treatment such as surgery or injectable drug at the RZL-012 injected area.


Intolerable Side Effect Definition
	
An intolerable side effect defined as any of the following treatment-related adverse drug reactions (ADRs):
 
 • Any Grade 3 or greater event except for the following (For the following events, a discussion will be held by the PI and the Medical Monitor to decide whether considered as an intolerable side effects): 
 ○ Flu-like symptoms and fever that responds to standard treatment within 72 hours ○ Localized edema and erythema ○ Pruritus ○ Pain ○ Skin/soft tissue inflammation ○ Fat Atrophy ○ Liver enzymes abnormality ○ Non-significant lab abnormalities, lasting less than 7 days (See Section 3.3.2) 
Subjects experiencing an intolerable side effect will be withdrawn from the study, but followed until the event resolves or becomes stable; all actions taken are to be fully documented in source documents and Case Report Forms (CRFs). To be considered an intolerable side effect, such an event must be considered to be possibly or probably related to the study drug
 
The study may also be prematurely terminated in any of the following cases:
 
 • Recurring serious or severe ADR clinically evaluated by PI as warranting study termination. • A decision made by Sponsor and/or Institutional Review Board (IRB)/Ethics Committee (EC) and/or local regulatory agency to terminate the study. 																								

Study Drug Dosage and Administration
	
The 1st cohort will be comprised of subjects with Dercum's disease: all subjects will be injected with RZL-012. Dosing will be calculated according to the size of the nodule (diameter) as determined by ultrasound: 5mg/cm² reaching a maximal dose of 40mg per subject (1/6.25 the No observed adverse effect level [NOAEL] based on Human Equivalent Dose [HED] from Good Laboratory Practice [GLP] toxicology study).
 
Nodule of 2-2.9cm diameter, as determined by ultrasound, will be injected 2 injections (0.1 mL each, 1 cm apart); total of 10 mg RZL-012.
 
Nodules of 3-3.9cm diameter, as determined by ultrasound, will be injected 3 injections (0.1 mL each, 1 cm apart); total of 15 mg RZL-012.
 
Nodules of 4-8cm diameter, as determined by ultrasound, will be injected 4 injections (0.1 mL each, 1 cm apart); total of 20 mg RZL-012.
 
  
 Cohort 1	
   
 Number of Subjects – Active	6	
 
 Nodule size – diameter (cm)	2-2.9	3-3.9	4-8	
 
 Total Dose of RZL-012 (mg)	10	15	20	
 
 Dose per NOAEL*	1/25th	1/18.75th	1/12.5th	
 
 Number of Injections	2	3	4	
  
 
Subjects will receive a single treatment in multiple sites (2-8) of injection according to the design in the picture below:
 
 
  
Lipoma size: 2-2.9cm 2 injections of RZL-012
 
 
  
Lipoma size: 3-3.9cm 3 injections of RZL-012
 
 
  
Lipoma size: 4-8cm 4 injections of RZL-012
 
 
	Cohort 1				Number of Subjects – Active	6			Nodule size – diameter (cm)	2-2.9	3-3.9	4-8	Total Dose of RZL-012 (mg)	10	15	20	Dose per NOAEL*	1/25 th	1/18.75 th	1/12.5 th	Number of Injections	2	3	4
Cohort 1																									
Number of Subjects – Active	6																								
Nodule size – diameter (cm)	2-2.9	3-3.9	4-8																						
Total Dose of RZL-012 (mg)	10	15	20																						
Dose per NOAEL*	1/25 th	1/18.75 th	1/12.5 th																						
Number of Injections	2	3	4																						

Injections will be diagonally (45 °) to the skin surface and towards the center of the nodule and the distance between injections in a nodule will be 1 cm (see picture below).

The 2nd cohort will be comprised of subjects with lipedema with substantial fat above the knee. The first 3 subjects will receive 30 mg RZL-012 in 6 injections (0.1mL each) in one leg followed by 30mg RZL-012 (6 injections, 0.1mL each) in the second leg adding up to 12 injections of 60mg RZL-012 (1/4.688th the NOAEL based on HED from GLP toxicology study). The last 3 subjects will receive 40mg RZL-012 in 8 injections (0.1mL each) in one leg followed by 40mg RZL-012 (8 injections, 0.1mL each) in the second leg adding up to 16 injections of 80mg RZL-012 (1/3.125th the NOAEL based on HED from GLP toxicology study).

Cohort 2		
Number of Subjects – Active	3	3
Total Dose RZL-012 (mg)	60	80
Dose per NOAEL*	1/4.688	1/3.125
Number of Injections	12	16

* based on HED from GLP toxicology study

A grid line will be drawn with a makeup pencil in a horizontal plane (Figure 2) 4-6 cm from the suprapatellar fat and its distance from the floor recorded. An attempt should be made to find palpable nodules along the grid line. The injection sites will be marked in circles with a non-erasable pen. This mark should be intensified upon following visits. Injections will be given in multiple sites (4-8 in each leg), diagonally (45 °) to palpable nodules, in the fat above the knee. An attempt should be made to lift the nodule and inject into the middle of the fat-mass. If no nodules are noted in the horizontal plane, drug will be injected in to the fatty tissue (in this case small nodules seen in ultrasound will be followed for changes). Injections will be on the same horizontal plane.

	
Injections will be spread as much as possible and the distance between injected sites will be at least 2-3 cm, according to the number of injections (see picture below).
  
12 injections of RZL-012 16 injections of RZL-012


Concomitant Medication
	
All concomitant medication given 1 month prior to study entry, including blood and blood products, dietary supplements, and non-prescription drugs will be listed at screening/baseline. The clinical significance of the medication use will be decided by the investigator. Study subjects will be routinely questioned for changes in the administration of concomitant medication during the trial and changes should be updated from medical records as well.
 
Subjects may not receive the following medications while on study:
 
 • Chronic treatment with systemic steroids or immunosuppressive drugs. • Chronic treatment with Non Steroid Anti-Inflammatory Drugs (NSAIDs) and aspirin. • Any investigational product other than RZL-012. 
Before dosing, analgesic gels or creams such Lidocaine (e.g., Emla) or Pramoxine should be used to numb the injected site. An ice pack may be applied on the site of injection following dosing to help reduce pain. At day 1 following injection, application of the anti-histamine Benadryl Gel (Diphenhydramine hydrochloride 1 %for topical use only) should be initiated prophylactically, according to drug instructions for use, to avoid itching at the injected area. Benadryl Gel should be applied for 7 days.
 
Use of nattokinase is prohibited and the use of other supplements or complementary medicines/botanicals should be approved by the PI, except for conventional multivitamin supplements. The use of prohibited supplements should be stopped a week before injection.

Study Procedure
	
Study activities upon study entry will include, but not be limited to: Informed Consent, full medical history, physical examination, vital signs measurements, ECGs, clinical laboratory tests, photography and skin irritancy evaluation of site injection, ultrasound, height and weight measurements, Quality of Life (QOL) and function questionnaire in lipedema subjects, and pain assessment.
 
Periodical site visits will allow assessment of treatment safety and efficacy. Subjects will be advised to keep their regular diet and physical activity.


Visit Schedule (See Table 2)
	
Subject site visits will be performed \pm 1 day from scheduled date for study visits Day 0-28 and $2\pm$ 1 days from schedule date for follow-up visits (Day 56). All data relevant for the visit needs to be obtained within 3 days (e.g., blood tests results) of visit.
 
Screening Day visit (Day -14 through -2):
 
 - Following signing the informed consent - assessment of subject eligibility will include: medical history, physical examination, vital signs, ECG, serology assays (HBV, HCV and HIV), clinical laboratory tests, drug screen. 
Clinical laboratory tests will include:

	
1. Hematology: Complete blood count (CBC) including White blood cell [WBC] differential values, Fibrinogen, and coagulation (International normalized ratio [INR], Partial thromboplastin time [PTT] and Prothrombin time [PT]).2. Serum chemistry analysis: sodium, calcium, potassium, phosphorus, glucose, liver enzymes (Aspartate aminotransferase [AST], Alanine aminotransferase [ALT], Lactate dehydrogenase [LDH], Creatine-kinase MM [CK-MM], Gamma-glutamyltransferase [GTPP], Alkaline phosphatase [ALP]), Bilirubin, Creatinine, Blood urea nitrogen [BUN], Total protein, Albumin, Amylase, Creatine phosphokinase [CPK], C-reactive protein [CRP]).3. Urinalysis: Nitrite, Sodium, Potassium, Calcium, Phosphate, Protein, Red blood cells (RBC), WBC, Blood, Glucose, Ketone bodies, Bilirubin, Urobilirubin, Urine specific gravity, Osmolality, and pH. 
- In addition, photography and evaluation of skin irritancy by Draize score of the injection site area.- For Dercum's disease subjects – ultrasound assessing nodules size (diameter) and quality. Determining which nodules are to be injected with a total of 40mg RZL-012.- For lipedema subjects – measurement of leg circumference above the knee and assessing fat thickness and nodular quality by ultrasound.- For lipedema subjects - QOL and function questionnaires. 
Baseline visit (Day 0):
 
- Pre-treatment: eligibility confirmation, vital signs, Draize score, leg circumference, clinical evaluation of local pain and tenderness to pressure and nodules size and/or numbers, blood sample for serum chemistry, and hematology baseline level will be taken.- Treatment - All injections will be administered 45 ° to the skin surface using a 1 mL Luer-lock syringe and a 30 G x 1/2" needle (the hole of the needle pointing into the fat layer).- Post treatment: ECG (4h and 8h ± 30min post injection), pulse rate (1h, 2h, 4h, 8h, 24h post injection in the opposite hand of blood sampling), vital signs (2h ± 30 min post injection), Draize score (2h post injection ± 30 min), adverse events (AEs) will be recorded. 
Schedule visits (Day 1-28):
 
- Day 1 following treatment will include: ECG, vital signs including pulse rate, Draize score, and photographs of the treated area, clinical evaluation of local pain and tenderness to pressure. Subjects will start applying an anti-histamine gel.- For safety reasons 24hr ± 2hr following injection, Blood samples for serum chemistry and hematology will be taken- Day 3 following treatment will include Serum chemistry and hematology.- Visits will take place every 7 days ± 1d from treatment till Day 28. During visits, all tests (physical exam, vital signs, ECG, clinical laboratory tests, urinalysis, Draize score, leg circumference above the knee, weight measurement, QOL and function questionnaires in lipedema subjects, clinical evaluation of local pain and tenderness to pressure and reduction in nodules size and/or numbers, photographs and ultrasound will be performed according to schedule (Table 2).- Subjects will be questioned for AEs every visit.- Subjects will record their daily use of analgesics. Diaries will be checked and data will be captured in the CRFs. 
Follow-up visit (Day 56):
 
- Subjects will be followed on Day 56 following injection.- A week before Day 56 visit, subjects will record their daily use of analgesics. Diaries will be checked and data will be captured in the CRFs.- Evaluation of the injected area will be performed by Draize score, photographs, QOL and function questionnaires in lipedema subjects, clinical evaluation of local pain and tenderness to pressure and reduction in nodules size and/or numbers.
--	---

	
 - For Dercum's disease subjects – ultrasound assessing nodules size (diameter) and quality. - For lipedema subjects – measurement of leg circumference above the knee and assessing fat thickness and nodular quality by ultrasound. - Subjects will be questioned for AEs.

Safety Analysis
	
Safety data from the study will be summarized descriptively by treatment and cohort. Descriptive statistics will be calculated for quantitative data and frequency counts and percentages will be provided for categorical data. The nature, frequency, seriousness, severity and relation to study drug of AEs will be tabulated for all subjects combined and by treatment. Change-from-baseline values for vital signs, clinical laboratory and ECG will be summarized. Shift tables of normal / abnormal versus baseline may be presented as well. Draize scores will be presented in tabular format by visit, treatment, and cohort. Serious adverse events (SAEs) will be described in narratives as part of the study report.

Study Endpoints
	
Primary Endpoint: Evaluation of the overall safety of RZL-012 injection into the subcutaneous fat in Dercum's disease and lipedema. The primary safety endpoint is the incidence of intolerable side effects.
 
Secondary Endpoints:
 
 1. For lipedema subjects - The reduction in local subcutaneous fat in the injection site region as compared to baseline based on ultrasound (reduction in nodules size and/or numbers) and leg circumference above the knee assessments. 2. For Dercum's disease subjects - The reduction in local subcutaneous fat in the injection site region as compared to baseline based on ultrasound (reduction in nodules size and/or numbers). 3. Extended duration of the fat reduction effect. To that end, ultrasound images and above the knee circumference measurement will be followed for 56 days. 4. Elucidation of the tissue changes by ultrasound of the injection site to include reduction in fat thickness and nodular quality. 5. Improvement in local pain as measured by Comparative Pain Scale and by the reduction in the use of analgesics. 6. Improvement in QOL and function in lipedema subjects as measured by questionnaire (such as The Lower Extremity Functional Scale (LEFS)).

Sample Size	This study is planned as a Phase 2a trial. A maximum of 12 evaluable subjects will be included in the study (6 Dercum's disease subjects and 6 lipedema subjects) and followed for as long as 56 days.
Statistical Methods	
Statistical analyses will be mainly descriptive in nature where study data will be tabulated and summarized using the mean, standard deviation or standard error, median, minimum, maximum and number of subjects by cohort for continuous data. For categorical data, results will be summarized via a count and percentage by cohort. The results will be presented overall, per cohort and per cohort and dose. The effects of noncompliance, dropouts, and covariates may be assessed to determine the impact on the general applicability of results from this study.
 
If any statistical tests are performed, they will be two-sided. The required significance level of findings will be equal to or lower than 5%. Nominal p-values will be presented.
 
Where confidence limits are appropriate, the confidence level will be 95%.
 
Incidence of intolerable side effects will be tabulated by study drug by cohort along with 95% confidence intervals.
 
Change from baseline will be presented in a tabular form by visit treatment.
 
AEs and tolerability data will be presented descriptively by treatment and cohort. AEs will be tabulated by body system, preferred term, seriousness, severity and relation to study drug by cohort. Where applicable, changes in values over time (e.g., lab values, vital signs, ECGs) will be presented; this will include clinical laboratory evaluations (including CBC, blood chemistry and urinalysis), coagulation (INR, PTT and PT), vital signs, and ECGs. Shift tables of normal / abnormal versus baseline may be presented as well.
 
Draize scores will be presented in tabular format by visit, treatment, and cohort

Study Duration	
Study duration is 2.5 months, including enrollment, treatment and follow-up period.
 
Each subject will participate in the study for up to 42 days as part of this protocol.

Study Site	University of Arizona Medical Center, Tucson, Arizona

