3.2. DOSE RATIONALE

The initial dose was determined by the NOAEL established by the Good Laboratory Practice (GLP) extended single dose toxicology study and by the previous phase 0 clinical trial in which 20mg RZL-012 was the highest dose achieved. This initial study is an escalating dose study. If no more than 1 subject experiences intolerable side effects within 14 days following the injection of the last dosed group, according to schedule, an additional cohort of volunteers will be administrated the next dose level.

Cohort 1- will be comprised of subjects with Dercum's disease. All subjects will be injected with RZL-012. Dosing will be calculated according to the size of the nodule (diameter) as determined by ultrasound: 5mg/cm² reaching a maximal dose of 40 mg RZL-012 per subject (1/6.25 the NOAEL based on the Human Dose Equivalent [HED] GLP Toxicology studies).

Cohort 2 - will be comprised of subjects with lipedema with substantial fat above the knee and will be conducted in a dose escalation manner.

The first 3 subjects will receive 60mg RZL-012 (1/4.688th the NOAEL based on HED from GLP toxicology study).

The last 3 subjects will receive 80mg RZL-012 (1/3.125th the NOAEL based on HED from GLP toxicology study).

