3.3. DOSING

3.3.1. Dosing Regimen

The dosing regimen will be a single dose treatment injection of RZL-012 in multiple sites.

Six subjects in cohort 1, all assigned to the RZL-012 treatment group will be dosed at a maximal dose of 40 mg RZL-012 (approximately 1/6.25th the NOAEL as determined in the GLP toxicology study). Dosing will be calculated according to the size of the nodule (diameter) as determined by ultrasound in a dose of 5mg/cm²:

Nodule of 2-2.9cm diameter, as determined by ultrasound, will be injected 2 injections (0.1 mL each, 1 cm apart); total of 10 mg RZL-012.

Nodules of 3-3.9cm diameter, as determined by ultrasound, will be injected 3 injections (0.1 mL each, 1 cm apart); total of 15 mg RZL-012.

Nodules of 4-8cm diameter, as determined by ultrasound, will be injected 4 injections (0.1 mL each, 1 cm apart); total of 20 mg RZL-012.

Cohort 1 – Dercum's disease			
Number of Subjects – Active	6		
Nodule size – diameter (cm)	2-2.9	3-3.9	4-8
Total Dose of RZL-012 (mg)	10	15	20
Dose per NOAEL*	1/25 th	1/18.75 th	1/12.5 th
Number of Injections	2	3	4

Six subjects in cohort 2, all assigned to the RZL-012 treatment group, will be dosed as follows:

The first 3 subjects will receive 30mg RZL-012 in 6 injections (0.1mL each) in one leg followed by 30mg RZL-012 (6 injections, 0.1mL each) in the second leg adding up to 12 injections of 60mg RZL-012 (1/4.688th the NOAEL based on HED from GLP toxicology study).

The last 3 subjects will receive 40mg RZL-012 in 8 injections (0.1mL each) in one leg followed by 40mg RZL-012 (8 injections, 0.1mL each) in the second leg adding up to 16 injections of 80mg RZL-012 (1/3.125th the NOAEL based on HED from GLP toxicology study).

*based on HED from GLP toxicology

Cohort 2 - Lipedema		
Number of Subjects – Active	2	2
Total Dose RZL-012 (mg)	60	80
Dose per NOAEL*	1/4.688	1/3.125
Number of Injections	12	16

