5. STUDY POPULATION

5.1. INCLUSION CRITERIA

Subjects meeting all of the following criteria will be eligible for study participation:

1. Post-menopausal (at least 2 years) women no more than 65 years old, with lipedema involving substantial fat above the knee or nodular Dercum's disease in such women and in men 20 - 65 years with nodular Dercum's disease.
2. For Dercum's disease subjects – at least 2 nodules to be injected of at least 2cm diameter each, as determined by ultrasound
3. For lipedema subjects - Significant subcutaneous fat above the knee as determined by circumference of 50cm
4. Generally considered healthy according to medical history, physical examination, ECG and laboratory evaluation with a special emphasis on metabolic parameters (fasting glucose concentration < 200 mg, normal blood pressure).
5. Subjects must be able to adhere to the visit schedule and protocol requirements and be available to complete the study.
6. Subjects must sign an informed consent indicating that they are aware of the investigational nature of the study.

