6.1.15. Adverse Events

The information obtained during weekly subjects questioning, review of subject's compliance record, physical examinations, vital signs measurements, blood testing, and by any other means will be evaluated in light of baseline medical data and thus provide the basis for adverse events identification and grading.

The trial will proceed within a cohort and from one cohort to the next as long as no more than one subject experiences intolerable side effects and based on the decision made by the PI. Proceeding from one subject to the next will be based on the decision made after reviewing all safety data collected by Day 7 within 2 ± 1 d of the last dosed subject in each cohort.

The AEs reported during the trial will be graded (see Section 9), documented, and assessed in light of their clinical significance and relation to investigational product. In addition, the following information regarding the AE must be obtained: AE description, start date, end date (if applicable) or ongoing, severity, seriousness, relationship to study drug, outcome (e.g., resolved / unresolved), and action taken (e.g., concomitant medication). The sponsor or the sponsor representative will provide information regarding serious adverse event (SAE) expectedness based on data included in the IB. AE monitoring will be conducted throughout subject's participation up to 56 days after injection.

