6.2.3. Study Treatment

6.2.3.1. Treatment with RZL-012 Investigational Therapy

[figure not shown]
RZL-012 is an investigational product supplied as a single dose single treatment injection in multiple sites (2-16) of injections. Before injection, subjects will be advised to keep their regular diet and physical activity.

The injection dosing regimen and technique is crucial for the therapy safety and efficacy. Syringes will be filled with 0.1 mL RZL-012 and the number of syringes will be compatible with the number of injections. All injections will be administered diagonally in 45 °, using a 1 mL Luer-lock syringe and a 30 G x 1/2" needle.

The hole of the needle should be pointing into the fat layer and the injection direction should be towards earth. An attempt to pull the plunger should be made before injecting to ensure that no blood is coming out. If so, the plunger should be pushed down to inject the medicine. The formulation is viscose, therefore resistance is expected while injecting.

[figure not shown]
For Dercum's disease - The 1st cohort will be comprised of subjects with Dercum's disease. Subjects will receive a single treatment in multiple sites (2-8) according to the design below (Figure 2).

Figure 1: RZL-012 Injection Design in Dercum's Disease Subjects

Injections will be diagonally (45°) to the skin surface towards the center of the nodule and the distance between injections in a nodule will be 1 cm (Figure 2).

Figure 2: RZL-012 Injection Sites in Dercum's Disease Subjects

For Lipedema - The 2nd cohort will be comprised of subjects with lipedema with substantial fat above the knee. A grid line will be drawn with a makeup pencil in a horizontal plane (Figure 3) 4-6 cm from the suprapatellar fat and its distance from the floor recorded. An attempt should be made to find palpable nodules along the grid line. The injection sites will be marked in circles with a non-erasable pen. This mark should be intensified upon following visits. Injections will be given in multiple sites (4-8 in each leg), diagonally (45°) to palpable nodules, in the fat above the knee. An attempt should be made to lift the nodule and inject into the middle of the fat-mass. If no nodules are noted in the horizontal plane, drug will be injected into the fatty tissue (in this case small nodules seen in ultrasound will be followed for changes). Injections will be on the same horizontal plane.

Figure 3: RZL-012 Injection in Lipedema

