8.4.2. Administration and Instructions for Use

Each individual vial must be kept and handled at room temperature.

The vial should be manually shaken before consumption.

1 mL Luer-lock syringes with RZL-012 solution should be filled with 30 G 1/2" sterile needle as described below:

- Cohort 1 - Dercum's disease subjects:

Nodule of 2-2.9cm diameter -will be injected 2 * 0.1 mL/syringe/nodule

Nodules of 3-3.9cm diameter - will be injected 3 * 0.1 mL/syringe/ nodule

Nodules of 4-8cm diameter - will be injected 4 * 0.1 mL/syringe/ nodule

In total -A maximum of 8* 0.1 mL/syringe/subject.

- Cohort 2 - lipedema subjects:

First 3 subjects: 6*0.1 mL/syringe/leg, a total of 12* 0.1 mL/syringe/subject.

Last 3 subjects: 8*0.1 mL/syringe/leg, a total of 16* 0.1 mL/syringe/subject.

One vial may be used for dosing of one subject. Breached vials will not be re-used for other subjects. Each vial must be placed back into the container. All open vials must be kept until the end of the study for the Sponsor to decide either to discard or return to the Sponsor.

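### Cohort 1's dose is written both as a 40 mg total and as a 40 mg ceiling, and nothing ties the move to cohort 2 to the doses delivered

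*Protocol*

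**What the plan says.** **Fixed total.** Under the Screening Day visit, the Synopsis visit schedule describes the nodule choice for Dercum's subjects as "Determining which nodules are to be injected with a total of 40mg RZL-012".

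**Ceiling.** The Synopsis dosing entry speaks of "reaching a maximal dose of 40mg per subject". Section 3.3.1 says the six subjects "will be dosed at a maximal dose of 40 mg RZL-012", and Section 8.4.2 gives the limit as "In total -A maximum of 8* 0.1 mL/syringe/subject". Section 3.2 and SAP 5.2.2 and 5.4.1.1 also word 40 mg as a maximum. Nodules of 2-2.9, 3-3.9 and 4-8 cm receive 10, 15 and 20 mg (2, 3 and 4 injections).

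**Entry.** Inclusion criterion 2 (Section 5.1) asks for "at least 2 nodules to be injected of at least 2cm diameter each, as determined by ultrasound". It sets no minimum combined size.

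**Sites.** Section 6.2.3.1 states: "Subjects will receive a single treatment in multiple sites (2-8) according to the design below".

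**Progression.** Section 3.2 calls the study dose-escalating and refers to "the previous phase 0 clinical trial in which 20mg RZL-012 was the highest dose achieved". Section 6.1.15 lets the trial move "from one cohort to the next as long as no more than one subject experiences intolerable side effects", subject to the Principal Investigator's decision.

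**Cohort 2.** The Synopsis, Sections 3.2, 3.3.1 and 8.4.2, and the SAP give 60 mg to the first three lipedema subjects and 80 mg to the last three. Section 6.2.3.1 gives 40, 60 and 80 mg to successive pairs.

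**Reporting.** Protocol Section 10.5.1 and SAP 5.8.2 promise results by cohort and dose. The cohort 1 row labelled as total dose (10, 15, 20 mg) is per nodule.

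**The concern.** Choosing nodules is the act that fixes a Dercum's subject's dose, and the text governing that choice disagrees with the text governing the dose. Read as a fixed total, it leaves some eligible subjects who cannot be dosed as described. Read as a ceiling, it allows cohort 1 subjects to receive no more than was already given in phase 0.

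This matters because Sections 3.2 and 6.1.15 let experience in cohort 1 support starting cohort 2. A count of subjects with intolerable side effects means something different at 20 mg than at 40 mg, and the rule for moving on does not mention dose. The same gap affects reporting: a breakdown by cohort and dose cannot be produced consistently for cohort 1 when the only printed dose categories belong to nodules rather than subjects.

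**Working it through.** **1. The ceiling reproduces.** A vial holds 250 mg in 5 mL (Section 8.2), or 50 mg/mL, so each 0.1 mL injection is 5 mg. Eight injections give 8 × 5 = 40 mg. The stated fraction agrees with the 20 mg row: 40 × 6.25 = 250 and 20 × 12.5 = 250.

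**2. Totals open to an eligible subject.** With exactly two nodules, each injected in full at its banded dose:

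| Nodule doses (mg) | Total (mg) | Injections |
|---|---|---|
| 10 + 10 | 20 | 4 |
| 10 + 15 | 25 | 5 |
| 10 + 20 | 30 | 6 |
| 15 + 15 | 30 | 6 |
| 15 + 20 | 35 | 7 |
| 20 + 20 | 40 | 8 |

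Only two nodules of 4-8 cm reach 40 mg. With more nodules, 40 mg can also be reached as 10+10+20, 10+15+15 or 10+10+10+10. A subject whose nodules are all 3-3.9 cm stops at 2 × 15 = 30 mg however many there are, because 3 × 15 = 45 exceeds the ceiling.

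**3. Site count.** Two nodules at no fewer than two injections each is 2 × 2 = 4. The lower end of the printed range, 2 sites (10 mg), cannot occur in a subject dosed in line with criterion 2.

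**4. Day 0 re-sizing.** Section 6.1.14 repeats the ultrasound before injection. A set chosen at screening as 10+15+15 = 40 mg becomes 10+15+20 = 45 mg (9 injections) if one nodule re-measures at 4.0 cm. The maximum rules out giving 45 mg, but nothing says how the nodules are then re-chosen.

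**5. Step into cohort 2.**
- 60/80 mg scheme: 60/40 = 1.5-fold if cohort 1 reached 40 mg; 60/20 = 3-fold if it stayed at 20 mg.
- Section 6.2.3.1 scheme: 40/40 = 1-fold or 40/20 = 2-fold, followed by 60/40 = 1.5-fold.

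**6. Chance that nobody in cohort 1 receives 40 mg.** Let q be the share of subjects able to reach 40 mg. The documents give no value, so q is an assumption, as is independence between subjects. Then P(none of 6) = (1 − q)^6.

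| q | P(none of 6 at 40 mg) |
|---|---|
| 0.10 | 0.53 |
| 0.20 | 0.26 |
| 0.25 | 0.18 |
| 0.50 | 0.016 |
| 0.75 | < 0.001 |

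**7. What a clean cohort would show.** With 0 events in n, the two-sided 95% exact upper limit is 1 − 0.025^(1/n). This is 45.9% for n = 6. If only 3, 2 or 1 subjects received 40 mg, the limit at that dose is 70.8%, 84.2% or 97.5%.

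**The case against.** The strongest reply is that cohort 1 was never meant as a 40 mg level. Its dose follows nodule size. Only cohort 2 is described as running by dose escalation, and Section 3.3.1 states the tolerability rule within a cohort and the next-level decision for cohort 2. A reader might infer a defined 40 mg step that the trial is bound to miss; no passage names one. What stands is narrower: the general escalation sentence in Section 3.2 and the cross-cohort rule in Section 6.1.15 do make cohort 1 a condition for cohort 2.

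Several other replies hold:
- Five of the six two-nodule combinations fall short of 40 mg, but that counts combinations, not patients. It does not show that most two-nodule subjects would fall short. The criterion is a minimum, and subjects with more nodules can reach 40 mg.
- The 45 mg case is not an authorised dose. Section 8.4.2 caps injections at eight, so what is missing is a re-selection rule.
- Under the ceiling reading a per-subject dose can be worked out as the capped sum of nodule doses. It is the table label and the reporting groups that are unclear.
- Dosing is staggered by at least 7 days, and progression also needs clinical judgement (the Principal Investigator, with the Medical Monitor in Section 3.3.1). SAP Table 14.2-1 and Listing 16.2.4-1 already cover drug administration.

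These safeguards reduce the risk, but none obliges the decision-makers to look at the doses delivered in cohort 1. The conflicting 40 mg start in Section 6.2.3.1 cannot be relied on as a safeguard while it remains unreconciled.

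**Conclusion.** The point holds as an inconsistency in operative dosing text that bears on a safety decision. The Screening Day wording conflicts with the ceiling stated everywhere else. The lower end of the site range conflicts with criterion 2. Cohort 1's dose groups for reporting are undefined. An eligible subject can receive from 20 to 40 mg, and nothing requires the delivered doses to inform the move to cohort 2.

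The consequence is conditional. Cohort 1 may add little or no exposure above 20 mg, which would make the next step up to 3-fold instead of 1.5-fold. This assumes whole-nodule dosing and the 60/80 mg scheme. How likely it is depends on nodule sizes that the documents do not give: across the assumed values of q, the chance that no subject reaches 40 mg runs from 0.53 to below 0.001.

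A reader might also conclude that the entry criterion must be tightened. That presumes a fixed dose, and under the ceiling reading criterion 2 can stay as it is. This should be fixed, but it does not invalidate the design.

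**What to change.** 1. Reconcile the Screening Day wording with the Synopsis dosing entry, Sections 3.2, 3.3.1 and 8.4.2, and SAP 5.2.2 and 5.4.1.1, so that one per-subject rule results. Which rule applies is for the sponsor to settle. Change criterion 2 only if that rule requires it.
2. Reconcile the 2 to 8 site count with criterion 2, and the lipedema scheme in Section 6.2.3.1 with the 60/80 mg scheme elsewhere.
3. State how nodules are re-selected when Day 0 re-sizing would take the banded sum past the stated maximum.
4. Label the cohort 1 table as dose per nodule, and define the cohort-and-dose grouping for cohort 1 by delivered mg per subject.
5. Have the record of the cohort 1 to cohort 2 decision list delivered mg for each subject.

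The cost is protocol and SAP wording plus one column in the review record and in Table 14.2-1. No patients, visits or procedures are added.
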